4.1 Duration of Study Participation

Participation in the main study may entail up to two years (24 months) of follow-up from the date of enrollment. The qualitative interview (Aim 2) will require only one day of participation to obtain informed consent and complete the interview.

4.2 Total Number of Subjects and Sites

We will seek to enroll about 1,980 women from a total of about 66 clusters in the Nyanza Region of Kenya. An average of approximately 30 women per cluster will be enrolled in the main study. Approximately 100 of these women will be selected to participate in an additional qualitative interview during the follow-up period. Among these 100 women, approximately 30 male partners will be selected and contacted to participate in a qualitative interview to learn more about how men perceive and use the HIV self-test kits. The total number of individuals enrolled in the study will therefore be approximately 2,010.

There are multiple sites contributing to this study. The University of Pennsylvania will serve as the prime implementing site, with the University of North Carolina and RTI International subcontracted to provide administrative and data management support until the transfer of study data to UPenn is complete. Impact Research and Development Organization (IRDO) is conducting all field work, including enrollments, follow-up, and monitoring for adverse events.

CONFIDENTIAL

4.3 Inclusion Criteria

High-risk women who meet with study staff will be screened for the following eligibility criteria after providing oral informed consent:

- Female
- Age ≥18 years
- Currently resides in the study area (hotspot or beach community)
- Has resided in the study area for at least 6 months in the year prior to enrollment
- Intends to stay in the region for at least 24 months
- Reports two or more sexual partners within the past 4 weeks
- HIV-negative*
- Ownership or access to mobile phone
- Willing and able to provide informed consent for participation
- Not enrolled in another HIV prevention research study

* To verify HIV status at baseline, women will be offered rapid HIV testing based on Kenyan guidelines. Those who test HIV-positive will be actively linked to care as per the IRDO drop-in center's protocol or the Ministry of Health recommendations.

4.4 Exclusion Criteria

Those who do not meet the inclusion criteria listed above, do not provide informed consent, or who do not provide oral consent to assess these eligibility criteria (screening) will be excluded from the study.

4.5 Subject Recruitment

Given the study's focus on reducing the risk of HIV acquisition among high-risk women in the study region, we will recruit HIV-negative women from the clusters that are selected for Aim 1. Our recruitment strategy closely resembles the strategy that we used to successfully recruit 101 HIV-negative FSW (over a one month period) for participation in a pilot study [22]. Specifically, from each hotspot we will recruit high-risk women including FSW enrolled in IRDO's drop-in center and others who meet eligibility criteria. We will rely on peer educators who have pre-existing relationships with these women to initiate contact, provide them with general information on the study, and refer those who are interested to meet with study staff. Peer educators will receive transport and outreach reimbursement for their recruitment activities. Recruitment will end when the target sample size is reached.

In the beach communities, we will obtain a sampling frame from the census of the study community which IRDO conducted towards the end of 2015; in addition, we will work with the beach management unit officials should we need additional information. We will then contact women to assess their eligibility to participate in the study. We will work with IRDO's program staff to identify those who may be eligible to participate in the study and refer them to the study venue if they are interested in learning more.

4.6 Vulnerable Populations:

Children, fetuses, neonates, or prisoners are not included in this research study. Pregnant women are neither excluded if they meet the other eligibility criteria, nor removed from the study if they become pregnant during the study. However, there are no study procedures that should affect the condition of the pregnant woman or fetus.

5 Study Procedures

Participants in clusters randomized to the intervention group will be provided with multiple self-tests over a period of up to 24 months and encouraged to distribute the tests to individuals in their sexual networks with whom they may have unprotected sex. Participants will be given several HIV self-tests *initially* and informed that they can obtain *additional* self-tests during the intervention period. Each self-test will include clear instructions for use, a list of HIV testing services (HTS) clinics where those obtaining reactive self-tests can seek confirmatory testing (as is recommended by Kenya's testing guidelines). In order to encourage individuals who obtain a reactive self-test to seek confirmatory testing *and* to measure uptake

CONFIDENTIAL

of confirmatory testing, a *VCT referral voucher* will be included with each self-test. Each self-test will also include a study phone number that participants or male partners of participants may call to obtain information about how to use the test and receive information on follow-up services.

At enrollment, participants will be trained on how to use HIV self-tests using methods and materials developed in our pilot study. They will be counseled on how to discuss HIV self-testing with sexual partners and on the importance of using their own discretion and assessing the risk of IPV when deciding whether to offer a self-test to a sexual partner. The concept of the HIV “window period” and the importance of condom use and other sexual risk reduction strategies will also be discussed. As part of the pilot study we carried out last year, we developed talking points for study staff to use when enrolling participants and giving them multiple self-tests. These talking points, as well as lessons we learned in the pilot study, will be fully incorporated into the education and counseling that participants will receive during enrollment. Participants will be reminded to use condoms whenever possible and reserve self-tests for primary partners as well as current and potential partners with whom unprotected sex is likely. The counseling message outlined in the study procedures discusses the rate of false negative results (up to 8%) that can occur when using the kits and gives possible reasons for false negatives to occur, including: improper use of the test, antibodies cannot be detected because of the window period, or the HIV positive person is on ARVs and virally suppressed. False positives are also explained such that any “reactive” test does not mean HIV positive and that any reactive test should be confirmed at a local VCT clinic for a proper medical diagnosis.

We will use the FDA-approved OraquickAdvance Rapid HIV-1/2 Antibody Test, which achieved 92% sensitivity in premarket self-testing in the US [44]. This oral fluid-based test detects antibodies to HIV-1 and HIV-2 in 20 minutes. Currently, the Oraquick self-test is approved for use in Kenya and the government is considering its broader use throughout the country. In our prior study, we developed easy-to-follow instruction materials on how to use the self-test. These instruction materials will be included with each self-test that is distributed to study participants.

Participants in the clusters randomized to the control group will be provided with several HTS referral vouchers initially and encouraged to distribute them to their sexual partners (participants will be informed they can return for additional vouchers during the follow-up period of up to 24-months. As in the intervention group, participants in the comparison group will also be counseled on the importance of condom use and other sexual risk reduction strategies. Female participants will also be encouraged to give their male partners a phone number that they can contact if they have questions.

For both study arms, research assistants will seek to recruit those who meet eligibility criteria. Research assistants will review the written informed consent form with eligible women and those who provide written consent to study enrollment will be administered a baseline questionnaire (described below), and digital fingerprint collection with a fingerprint biometric device to verify identification at follow-up visits. We have found fingerprinting to be highly acceptable, and it has been successful in other studies in the region.

Data Collection Procedures:

Baseline data. At the time of enrollment, participants will be administered a baseline questionnaire to record information such as socio-demographic characteristics, economic characteristics, sexual behavior, HIV testing history, and any experience of IPV.

Distribution Visits. Participants will be offered the opportunity to collect additional HIVST or VCT referral coupons regularly during the follow-up period. These visits will entail the distribution of the study tools, retraining on important counseling messages (how to safely avoid IPV, importance of condom use, etc.) and collect basic information on how the study tools previously distributed were used. IPV and other possible adverse events will be monitored at every point of contact.

5.1 Screening and Baseline Visit

At the screening and baseline visit, which occurs on the same day, the following procedures are performed:

- Verbal informed consent obtained to screen for eligibility
- Screening questions administered by research assistant
- HIV rapid test is performed according to Kenyan HTS guidelines. Currently, this includes testing with Alere Determine HIV-1/2 rapid antibody test and confirming all non-negative results with Premier Medical Corporation First Response HIV 1-2 rapid antibody test. Appropriate counseling is provided by research assistants, who are certified HTS counselors by the Kenyan government.
- Main study written informed consent obtained

CONFIDENTIAL

- Fingerprinting enrollment process
- Administration of the baseline visit questionnaire
- Distribution of the HIV self-test kits or HTS referral cards, including counseling on how to safely use and distribute the intervention.
- Reimburse participant for travel and time

The screening and baseline visit is estimated to take approximately 90 minutes.

5.2 Follow-Up Visits

5.2.1 Monthly Distribution Visits

Each month, research assistants will schedule a time to visit each cluster where enrollments have taken place. Participants will be made aware of the venue and times that the research assistant will be available, and they can attend the event to replenish their stock of either HIVST kits or HTS referral cards. Fingerprints are collected to verify the participant's identity and a record is kept of the serial number of the HIVST kits or referral cards. Participants will be asked how they used and distributed to cards to help guide additional discussion about the number of HIVST kits or VCT referral cards to receive and if relevant counseling messages need to be reiterated. The research assistants will also use this time to answer any questions about the study, intervention use, distribution, or adverse event reporting that the participants would like to discuss. Participation in the monthly distribution visits is optional; if participants do not need to replenish their supply, have no questions, or cannot attend, there is no additional follow-up for these visits. These visits will take approximately 10 minutes, on average.

5.2.2 6-Monthly Follow-Up (Months 6, 12, 18, and 24)

The 6-monthly follow-up procedures will be used to test for HIV, collect information about the use of the interventions, and address any questions the participant may have. These visits will take approximately 45 minutes. Specific procedures include:

- Fingerprint verification of participant's identity
- HIV rapid test is performed according to Kenyan HTS guidelines.
- Administration of the follow-up visit questionnaire
- Distribution of the HIV self-test kits or HTS referral cards, to include "refresher" counseling session on how to safely use and distribute the intervention.
- Reimburse participant for travel and time

5.2.3 Qualitative Interview Visits

Approximately 100 women and 30 male partners of women selected will be invited to participate in qualitative interviews. This interview will examine the person's experience with the HIVST or referral vouchers. It will occur one or two times and take approximately 60 minutes each time. Specific procedures include:

- Informed Consent (men only: qualitative interview is described in the main study consent that female participants will sign at the baseline visit)
- Interview with research assistant
- Identify sexual partners who may be willing to participate in qualitative interview (female only to identify 30 men)
- Reimburse participant for travel and time

5.2.4 End of Study Visit

The end of study visit is identical to the last 6-monthly follow-up visit. No results will be shared with the subject at this time, and no unblinding is necessary.

CONFIDENTIAL

5.3 *Unscheduled Visits*

Unscheduled contact with the participant will occur most often through the study hotline number. This number is provided on the informed consent, HIVST instruction sheet, on the confirmatory testing card, and on HTS referral card. If an in-person meeting is necessary, the Study Coordinator, who manages the hotline number, will schedule a time for the participant to meet with a research assistant. All meetings will be documented in a note to file which is placed in the participant's file at the IRDO office. If the meeting is to report an adverse event, appropriate steps will be taken to notify the PI's and IRB offices.

5.4 *Subject Withdrawal*

Subjects may withdraw from the study at any time without impact to their care. They may also be discontinued from the study at the discretion of the Investigator for lack of adherence to intervention or study procedures or visit schedules, and AEs. The Investigator or the Sponsor may also withdraw subjects who violate the study plan, to protect the subject for reasons related to safety or for administrative reasons. It will be documented whether or not each subject completes the study.

5.4.1 *Data Collection and Follow-up for Withdrawn Subjects*

No additional data will be collected or follow-up attempted for participants who withdraw completely from the study.

5.5 *Early Termination Visits*

The last 6-monthly follow-up survey form will serve as the final data collection for participants who withdraw. No additional data will be collected or follow-up attempted for participants who terminate their involvement with the study.

5.6 *Safety Evaluation*

To ensure correct usage of self-tests (in the intervention group) and to minimize the probability of psychological distress due to HIV testing, we will include simple instruction materials with each self-test on how to use the tests, in English and local languages. These instruction materials have been developed by us and used in our pilot study, and they were well-received by FSW and the sexual partners. In addition, each self-test will include clear information on the importance of seeking confirmatory HIV testing (which is recommended by the WHO and the Kenyan Ministry of Health) – as such the vouchers and self-test will include information listing HTS clinics in the area where free HIV testing and counseling is available. Information will also be provided on clinics in the area where free HIV care and treatment is available. We will also establish a support telephone line (hotline) that study participants or their sexual partner can call at any time that will put them in touch with the study coordinator, who will be ready to provide additional information on where to seek further testing, care or treatment.

IPV is monitored at each in-person visit, through the monthly text-message based survey, and by providing the 24/7 hotline for self-reporting. The Study Coordinator who mans the hotline and is responsible for first contact for all IPV reports will provide information and resources to the woman to include emergency medical treatment, support hotlines to call, and additional resources as necessary. All incidences of IPV will immediately be reported to the PI's and those related to the study intervention will be reported to both IRBs within one day.

6 *Statistical Plan*

6.1 *Sample Size and Power Determination*

We will seek to enroll about 1,980 women from a total of about 66 clusters. An average of approximately 30 women per cluster will be enrolled in the study. The power analysis for this cluster randomized study focused on the primary outcome comparing HIV infection incidence among high-risk women between two groups: the comparison group receiving vouchers for in-clinic HIV testing vs. an intervention groups receiving oral fluid-based HIV self-testing kits. Assuming an annual HIV infection incidence of 0.045 in the control group, the sample size required to detect a 50% reduction in this incidence with 80% power and a

CONFIDENTIAL

type I error of 0.05 is 1,980 women, with 33 clusters per study group and 30 women per cluster. This calculation assumes a 10% loss to follow-up over 1.5 years of follow-up and a coefficient of variation of 0.40 [48,49]. 1.5 years of follow-up is conservatively assumed for the power calculation, as this is the expected amount of time that FSWs will be followed, even though there is a maximum of 2 years.

6.2 Statistical Methods

6.2.1 Analysis of Primary Outcome of Interest

The annual incidence of HIV infection will be compared between study arms through regression modeling using a generalized estimating equations (GEE) approach with a log link and assumed Poisson response distribution (the negative binomial distribution will be used if this distribution is not valid). An offset will be used in this model to account for differential follow-up times. The model will contain a dichotomous covariate for study group; the two-sided ($\alpha = 0.05$) statistical significance of the associated regression coefficient will be assessed with a Wald test performed using robust standard errors. If there are differences in baseline characteristics between the two study groups, a second regression model will be constructed that adjusts for the differing baseline characteristics.

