Promoting awareness of serostatus is especially important among *high risk populations* such as women who have multiple partners, such as women engaging in transactional sex, as well as their sexual partners. The vulnerability to HIV of women who engage in transactional sex has been extensively documented [9]. Female sex workers (FSW) in SSA have HIV prevalence that often exceeds 50% and is 10-20 times higher than prevalence in the general population [10, 11]. HIV prevalence among FSW in the proposed study setting is estimated to be 56.5% [12] and recent data indicate there are 534 active FSW “hotspots” of commercial sex work, with an estimated 4,041 FSW [13]. Fisher folk communities (FFC) – also referred to as beach communities – similarly have a higher burden of HIV-1 infection than respective general populations [14-16]. Studies have reported HIV prevalence between 25–29% and annual incidence rates of 3.39-4.9% in Kenyan and Ugandan FFC. These figures are 3–4 times higher than respective national averages. Unlike general populations, fishing communities tend to be socially marginalized and often stigmatized. Due to ready cash from fishing activities coupled with staying away from their spouses and other family, FFC are characterized by a high presence of bars, lodges and

CONFIDENTIAL

entertainment halls, transactional sex (sex for money and sex for fish), high alcohol consumption and multiple sexual partnerships, but very limited access to health services.

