3.1 General Design

We will conduct a cluster randomized trial among HIV-negative women in the Nyanza region of Kenya. Clusters will be defined as hotspots where women exchange sex and FFCs along beaches in the study region. Clusters will be randomized to an intervention group in which women will be given *multiple* HIV self-tests coupled with referral vouchers for confirmatory testing (for those obtaining an HIV-positive result) or to a comparison group that is given multiple referral vouchers alone for clinic-based HIV testing. We will test for HIV and collect survey information, including sexual behaviors and HIVST use, from women at a baseline visit and every six months for up to 24 months.

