3.2 Allocation to Interventional Group

Clusters of geographic areas will be matched on the basis of population and type (hotspot for women who exchange sex or beach community) and then randomized to two study groups (receiving HIV self-test kits or referral cards for HTS based testing) in a 1:1 ratio. Computer-generated randomization will be used to determine group assignment of clusters. There will be no blinding associated with the study.

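### The primary GEE omits the matching factors and states no small-sample correction, so its type I error is about 6% or just under 5%, depending on how prognostic those factors are

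*Combined protocol and SAP*

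**What the plan says.** Section 3.2 restricts the randomisation: "Clusters of geographic areas will be matched on the basis of population and type (hotspot for women who exchange sex or beach community"), followed by 1:1 allocation. Section 3.1 fixes the unit: "Clusters will be defined as hotspots where women exchange sex and FFCs along beaches in the study region".

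Section 6.2.1, repeated in the Study Summary, specifies a Poisson GEE with log link and a follow-up offset. "The model will contain a dichotomous covariate for study group", and its two-sided 0.05 significance "will be assessed with a Wald test performed using robust standard errors". A second model adjusts for baseline characteristics, but only for those found to differ between groups. Neither place names the unit for the robust standard error, a small-sample correction or a t reference, and neither brings population or type back.

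Section 6.1 gives the design inputs: "Assuming an annual HIV infection incidence of 0.045 in the control group", a 50% reduction, 80% power, "33 clusters per study group and 30 women per cluster", 10% loss, 1.5 years of follow-up and a coefficient of variation of 0.40.

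**The concern.** Matching makes the arms alike on type and population. If those factors predict incidence, the estimated rate ratio varies less from one randomisation to the next than it would without matching. A model containing only study group cannot see this, so its standard error is too large and the test is conservative. Separately, an uncorrected sandwich estimate with a normal reference is somewhat too small with 33 clusters per arm, which makes the test liberal.

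The conditional second model does not settle this, because matching tends to prevent the very imbalance that would trigger adjustment for its own factors. What is at stake is calibration: the level of the single primary test is then set by an unknown, the prognostic strength of the matching factors, and not held at 5% by design.

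**Working it through.** **1. The plan's own sample size.** Person-years per cluster: 30 × 1.5 × 0.9 = 40.5. The unmatched cluster formula is

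c = 1 + (1.960 + 0.842)² × [(λ0 + λ1)/y + k²(λ0² + λ1²)] / (λ0 − λ1)²

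With λ0 = 0.045, λ1 = 0.0225, k = 0.40 and y = 40.5, the bracket is 0.001667 + 0.000405 = 0.002072. Dividing by 0.00050625 gives 4.092; times 7.849 gives 32.12; c = 33.12. The stated 33 per arm is reproduced (79.9% power at 33). The matched version of the formula gives 34.1. Without the added cluster, 0.0225/√(0.002072/33) = 2.840 and Φ(2.840 − 1.960) = 81.1% power.

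**2. Why the net effect is small.** Under no effect, the variance of one cluster's log rate is about 1/(0.045 × 40.5) + 0.40² = 0.549 + 0.160 = 0.709. Even perfect matching removes only 0.160/0.709 = 23% of it. If the matching factors carry a share s of between-cluster variance, the large-sample level of the arm-only test is 2[1 − Φ(1.96 × √(0.709/(0.709 − 0.160s)))]: 5.0%, 4.4%, 3.7% and 2.6% at s = 0, 0.25, 0.5 and 1. Simulation of the planned test with 33 matched pairs, which adds the small-sample error, gives 5.9%, 5.2%, 4.5% and 3.2%.

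**3. Plausible shares.** No hotspot incidence is given. Section 1.1 cites "annual incidence rates of 3.39-4.9% in Kenyan and Ugandan FFC". Assume this applies to trial women at beaches, that 0.045 is the average over both types, and that the split is equal. The hotspot:beach ratio is then (0.09 − b)/b:
- b = 0.0339: 1.65
- b = 0.04145 (midpoint): 1.17
- b = 0.049: 0.84

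The share on type is about [(r − 1)/(r + 1)]²/0.16. For r = 1.65 that is (0.65/2.65)²/0.16, about 0.37. Ratio 2.0 lies outside the cited range and serves as an outer bound.

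**4. Simulation.** 40,000 trials per cell (Monte Carlo error about 0.1 points for type I error, 0.2 for power); 17 hotspots and 16 beaches per arm; pairs within type on population; population given no effect; 40.5 person-years in every cluster; total CV 0.40; independence Poisson GEE by cluster. The correction is Kauermann-Carroll with t on 64 df (arm only) or 62 df (adjusted). Entries are %.

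| Hotspot:beach ratio | 0.84 | 1.0 | 1.17 | 1.5 | 1.65 | 2.0 |
|---|---|---|---|---|---|---|
| Share of variance on type | 5 | 0 | 4 | 25 | 37 | 68 |
| Type I error, as written | 5.8 | 5.9 | 5.7 | 5.1 | 4.7 | 4.0 |
| Type I error, covariates only | 6.4 | 6.3 | 6.2 | 6.2 | 6.1 | 6.3 |
| Type I error, correction only | 5.0 | 5.1 | 4.9 | 4.3 | 4.0 | 3.3 |
| Type I error, both | 5.1 | 5.2 | 5.0 | 4.9 | 4.9 | 5.0 |
| Power, as written | 83.4 | 83.3 | 83.2 | 83.9 | 83.7 | 84.6 |
| Power, both | 81.7 | 81.4 | 81.6 | 83.2 | 83.5 | 85.7 |

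Corrected arm-only power at ratio 1.0 is 81.4%, close to the 81.1% in step 1. So the roughly 2 extra points as written reflect the inflated level. Repeat simulations at the same inputs gave, as written, 5.5 to 5.9% at ratio 1.0, 4.7 to 4.9% at 1.65 and 3.8 to 4.3% at 2.0. With both changes they gave about 4.6 to 5.2%, apart from one 20,000-trial run at 5.4% (ratio 2.0).

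**5. Sensitivity.**
- Split, at the lowest beach rate. With 22 hotspots and 11 beaches per arm (ratio 1.49), type I error is 5.4% as written and 5.0% with both changes. With 11 and 22 (ratio 1.98), it is 3.8% and 5.0%.
- Unequal person-time (assumed, since section 6.1 gives only an average cluster size). At CV 0.5 and ratio 1.0, type I error is 6.4% as written and 5.4% with both changes; power is about 82% and just under 80%. At CV 0.8, type I error is 6.8% and 5.8%.
- Between-cluster CV. Over shares from 0 to 100%, the as-written level runs from 5.6 to 4.4% at CV 0.25 and from 6.2 to 1.9% at CV 0.60.

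**The case against.** The case for leaving the plan alone is a fair one. Over the cited incidence range with an equal split, the level is 4.7 to 5.9%, within one point of nominal. The sample size reproduces with the unmatched formula, so design and arm-only analysis agree with each other. Where matching is prognostic, ignoring it errs on the safe side. The phrase on robust standard errors does not exclude a correction; it leaves the matter unspecified. Other valid analyses exist: a matched-pair t test on 32 df held 4.9 to 5.1% with equal cluster sizes.

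The ratios are also constructed. The cited incidence describes fishing communities, whereas every trial woman "Reports two or more sexual partners within the past 4 weeks", so the real contrast may be smaller. Section 6.1 does not say that 0.045 averages over both cluster types, and section 3.2 does not say whether matching is in pairs or strata.

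All of this stands, and it keeps the point minor. It does not remove it: if the factors turn out uninformative, the test as written runs at about 6%, and nothing in the plan prevents that.

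A reader might also infer that the analysis ignores clustering because the robust unit is not named. The documents do not support that: sections 3.1 and 6.1 make the randomised cluster the natural reading, so this is only a gap in wording.

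**Conclusion.** The point holds as a minor one. On the assumptions in the working, the planned test has a type I error of about 6% if type and population do not predict incidence, and just under 5% at the strongest contrast implied by the cited beach rates. The two errors partly cancel, and which one prevails depends on a quantity the documents do not give.

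Four stronger readings are not supported:
- **That the level plausibly ranges down to 4%.** That needs a ratio near 2.0 or a beach-heavy split with the lowest beach rate. A prognostic population effect would push the same way, but no figure for it is given.
- **That the estimate is biased.** It is not; only its standard error is affected.
- **That planned power is in danger.** Power as written was at or above about 80% in every scenario where it was computed.
- **That the remedy guarantees 5%.** With equal clusters it comes close. With unequal person-time it improves the level without fully restoring it: about 4.7 to 5.4% at CV 0.5 and about 5.8% at CV 0.8.

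**What to change.** In section 6.2.1 and the Study Summary:
1. Name the randomised cluster as the unit for the GEE and the robust standard error.
2. Include cluster type and the population measure (or size strata) used for matching in the primary model.
3. Together with item 2, use a small-sample-corrected sandwich standard error with a t reference, for example Kauermann-Carroll on clusters minus parameters (66 − 4 = 62 df with type and one population term).
4. Report the unadjusted rate ratio alongside.

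Items 2 and 3 must go together. The covariates alone gave 6.1 to 6.4%; the correction alone leaves the test conservative if type is prognostic (4.0% at ratio 1.65).

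The cost is SAP wording, keeping the population figures used for matching in the analysis dataset, and two degrees of freedom (more if several size strata are used). If the factors are not prognostic, power falls by about 2 points against the plan as written: about 83% to 81% with equal clusters, and about 82% to just under 80% at a person-time CV of 0.5. If they are prognostic, there is little loss or a gain. With a log link the rate ratio keeps its meaning.
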